##### **3.1.3. Pharmacodynamic/Pharmacokinetic Analysis Sets**

The pharmacodynamic/pharmacokinetic analysis sets include data from subjects in the ITT analysis set who have the necessary baseline and on-study measurements to provide interpretable results for the specific parameters of interest.

#### **3.2. Subject Groups**

There is only 1 treatment group for this study.

#### **3.3. Treatment Strata**

There is only 1 treatment group for this study and no treatment strata were planned. However, given the increasing relevance of bendamustine as a component of treatment for subjects with iNHL, the IWRS will gate  $\leq 50$  subjects without prior bendamustine treatment.

### **3.4. Examination of Subject Subsets**

The efficacy endpoints (ORR, DOR, TTR and PFS) will be examined in the following subject subsets:

- Refractory to last therapy status (Yes or No)
- Number of prior therapies (<4 or  $\geq$ 4)
- Number of times refractory to an Alkllating Agent ( $\leq$  1 or  $>$  1)
- Number of times refractory to Rituximab ( $\leq$  2 or  $>$  2)
- Refractory to bendamustine (Yes or No)
- Disease subcategory (FL, SLL, WM or MZL )
- Suite for radioimmunotherapy (Yes or No)
- Bulky status (Longest diameter of baseline lesion  $<$ 7cm or  $\geq$  7cm)
- Gender (Male or Female)
- Age group (<65 or  $\geq$ 65 years)
- Race (White or Non-White)
- Region (US or Non-US)

AEs will be examined in the following subject subsets:

- Sex (Male or Female)
- Age group (<65 or  $\geq$ 65 years)
- Race (White or Non-White)
- Region (US or Non-US)

### **3.5. Multiple Comparisons**

Not applicable.

### **3.6. Missing Data and Outliers**

#### Missing Data

A missing data point for a given study visit may be due to any of the following reasons:

- A visit occurred in the window but data were not collected or were unusable
- A visit did not occur in the window
- A subject permanently discontinued from the study before reaching the window

In general, values for missing data will not be imputed unless methods for handling missing data are specified.

Missing data in Functional Assessment of Cancer Therapy: Lymphoma (FACT-Lym) will be handled according to the administration and scoring guidelines (Section 6.4.2.5).

### **Outliers**

No data will be excluded from the analyses, including any outliers.

### **3.7. Data Handling Conventions and Transformations**

- By-subject listings will be presented for subjects in the ITT analysis set and sorted by subject number, visit, and time (if applicable).
- Summary tables for continuous variables will contain the following statistics: N (number in analysis set), n (number with data), mean, standard deviation (StD), 95% CI, median, Q1, Q3, minimum, and maximum. The same number of decimal places as in the raw data will be presented when reporting minimum and maximum, 1 more decimal place than in the raw data will be presented when reporting mean, median, Q1 and Q3, and 2 more decimal places than in the raw data will be presented when reporting StD and 95% CI.
- Summary tables for categorical variables for baseline and safety data will include: N, n, percentage. The tables for efficacy endpoints will include standard error, and 95% CIs on the percentage, where appropriate. Unless otherwise indicated, 95% CIs for binary variables will be calculated using the binomial distribution. The denominator for the percentages will be the number of subjects in the respective analysis set, unless otherwise specified. Missing data will be included as a row in tables where it is appropriate. All percentages will be presented as one-decimal point, unless otherwise specified. Percents equal to 100 will be presented as 100% and percents will not be presented for zero frequencies.
- Data from all sites will be pooled for all analyses.
- Unscheduled visits will only be included in listings and the best or worst post-baseline summary. Unscheduled visits will not be included in the by-visit summary tables, unless otherwise specified.

- Unless otherwise specified, all analyses will be 2-sided at the 0.05 level of significance.
- For Kaplan-Meier (KM) estimates, the 95% CIs will be calculated using Greenwood's formula with (complementary) log-log transformation.

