#### Study Procedures and Timingc

a Required at screening. If disease present at baseline, to be performed post-baseline to confirm response category in subjects with potential CR by radiological assessments. If the baseline bone marrow biopsy/aspirate does not show lymphoma involvement, it is not necessary to obtain a follow-up bone marrow biopsy/aspirate to establish CR.

b For subjects with LPL only, performed locally per standard of care

c For detailed information regarding activities to be performed at each visit, see Section 7.2 of study 101-09 protocol.

**Abbreviations:** β-HCG, beta human chorionic gonadotropin; HRQL, health-related quality of life; FACT-Lym, Functional Assessment of Cancer Therapy- Lymphoma; ECG, electrocardiogram; CT, computed tomography; LPL, lymphoplasmacytoid lymphoma; MRI, magnetic resonance imaging; SPEP, serum protein electrophoresis; CR, complete response

Randomization	No randomization will be performed in the study.
Site and/or Stratum Enrollment Limits	
Study subjects will be enrolled at investigational sites in North America and Europe.
 
At least 50 subjects with prior bendamustine exposure will be enrolled. The IWRS will gate accrual of subjects without prior bendamustine treatment.

Study Duration	
All subjects may receive study drug indefinitely unless any of the withdrawal criteria (such as withdrawal of consent, experienced an adverse event, or tumor progression) indicated in Section 9 of the protocol is met.
 
Subjects will be followed in the clinic at 2-week intervals through the first 12 weeks of treatment, at 4-week intervals from 12 to 24 weeks of treatment, at 6-week intervals from 24 to 48 weeks of treatment, and at 12-week intervals thereafter. Tumor response will be evaluated at baseline; at 8, 16, and 24 weeks of therapy; and every 12 weeks thereafter according to standard criteria. The responses will be assessed by both the investigator and an independent review committee (IRC), with the IRC-reviewed responses treated as primary in the efficacy analyses.
 
Enrollment is planned to occur over <math>\leq</math> 15 months; subject follow-up will continue through <math>\geq</math> 6 months.

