### **7.2.5. Transaminase elevations**

Analysis of transaminase elevations will be based on laboratory values. Number and percentage of subjects will be summarized for subjects

- with Grade 3 or 4 ALT/AST elevation
- with Grade 3 or 4 ALT/AST elevation resolved to both ALT/AST of Grade 1 or less
- re-challenged after dose interruption due to Grade 3 or 4 ALT/AST elevation

- with recurrence of grade 3 or 4 ALT/AST elevation
- with recurrent Grade 3 or 4 ALT/AST elevation resolved to both ALT/AST of Grade 1 or less

Kaplan-Meier curves and estimates will be provided for time to onset of first Grade 3 or 4 treatment-emergent ALT/AST elevations. Time to onset of first event is defined as time from start of study treatment to the start date of first Grade 3 or 4 treatment-emergent ALT/AST elevation, ie, time in days is calculated as (start date of first occurrence) – (date of first dose of study drug) +1. In the absence of an event, the censoring date applied will be the earliest from the following dates: last dose date (if treatment discontinued) + 30 days, analysis data cut-off date and death.

For subjects with at least 1 episode of Grade 3 or 4 ALT/AST elevation, time to resolution of first episode of treatment-emergent Grade 3 or 4 ALT/AST elevation to Grade 1 or less will be summarized using Kaplan-Meier estimates. The same censoring rule described above for time to onset will be used. In addition, the same analysis will be performed for subjects who are rechallenged due to Grade 3 or 4 treatment-emergent ALT/AST elevations.

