### **7.6.1.           Corrected QT Intervals**

Corrected QT (QTc) intervals will be derived by using Bazett and Fridericia methods:

Bazett:  $QTc-B = QT / (RR)^{1/2}$ , and

Fridericia:  $QTc-F = QT / (RR)^{1/3}$ ,

Where, RR is calculated as [60 / Heart Rate (beats/min)].

The QTc data (msec) obtained by using the Bazett and Fridericia corrections will be categorized separately into the following classifications and summarized by visit:

- $\leq 450$
- 451–480
- 481–500
- $> 500$

The change in QTc values (msec) obtained by using the Bazet's and Fridericia's correction will also be categorized separately as follows:

- $\leq 30$
- 31-60
- $> 60$

QTcB, QTcF, and uncorrected QT values at each visit and change from baseline at each visit will be summarized for the ITT analysis set using descriptive statistics (sample size, mean, standard deviation, median, Q1, Q3, minimum, and maximum).

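### Read literally, the SAP 3.7 rule on unscheduled visits keeps unscheduled ALT/AST results out of the onset, resolution and recurrence analyses of 7.2.5, so events first seen at such tests can be dated late or missed

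*SAP*

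**What the plan says.** SAP Section 3.7, in its list of data-handling conventions, rules: "Unscheduled visits will only be included in listings and the best or worst post-baseline summary". The next sentence adds: "Unscheduled visits will not be included in the by-visit summary tables, unless otherwise specified". The exception clause stands in that second sentence, on by-visit tables. The first sentence has none.

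Section 7.2.5 then sets out the liver analyses. On the data source it says only this: "Analysis of transaminase elevations will be based on laboratory values". It plans a Kaplan-Meier analysis of onset, defined as "time from start of study treatment to the start date of first Grade 3 or 4 treatment-emergent ALT/AST elevation". It plans a second one of "time to resolution of first episode of treatment-emergent Grade 3 or 4 ALT/AST elevation to Grade 1 or less", repeated for rechallenged subjects. It also plans counts of subjects whose Grade 3 or 4 elevation resolved, recurred, or resolved after recurrence. It does not say whether unscheduled results are used.

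Scheduled chemistry follows the visit calendar in Section 1.2: every 2 weeks to Week 12, every 4 weeks to Week 24, then "at 6-week intervals from 24 to 48 weeks of treatment, and at 12-week intervals thereafter".

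**The concern.** Onset, resolution and recurrence are read from the dated sequence of ALT/AST values. None of them is a listing, and none is a best or worst value. A programmer who applies 3.7 as written would build the 7.2.5 datasets from scheduled visits alone.

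Two things are at stake. First, an event first seen between scheduled visits would be moved to a later visit or lost. Section 7.2.5 counts time in days from the date of the first occurrence, and scheduled visits 6 or 12 weeks apart cannot support that precision. Second, two tables of the same report could disagree about the same subject. The worst-grade summary may use an unscheduled value; the onset analysis may not.

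**Working it through.** **1. Is each 7.2.5 analysis allowed to use unscheduled values under 3.7?**

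- Kaplan-Meier time to onset (Table 3.2.2.5): not a listing and not a best/worst summary, so excluded.
- Kaplan-Meier time to resolution (Table 3.2.2.5): excluded for the same reason.
- Counts of resolution and recurrence (Table 3.2.2.4): they need the order of values, not the extreme value, so excluded.
- Count of subjects with any Grade 3 or 4 elevation: can be read as a worst-value summary, so arguably included.
- Worst post-baseline grade (7.2.3.2, Table 3.2.2.2) and shift to worst grade (7.2.4): included.

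**2. Does other text re-admit them?** Section 7.2 says that summaries use observed data, which does not address visit type. Section 7.2.3.1 defines treatment-emergent abnormalities over a period (first dose to 30 days after the last) and is silent on visit type. The statement in Section 3.6 that nothing is excluded from the analyses stands under Outliers. None is an express exception.

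**3. Size.** The SAP states no figure to reproduce. The intervals L come from the study days in the Section 1.2 schedule: 15 − 1 = 14, 113 − 85 = 28, 211 − 169 = 42, and 12 × 7 = 84 days after Week 48. These are nominal; visit windows shift them slightly.

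Assumptions, not in the SAP: onset is uniform within an interval, and an unscheduled test sees the episode at its start. For an episode that lasts at least one interval, mean dating delay = L/2 and the maximum is about L. An episode of d days falls wholly between two scheduled visits with probability max(0, 1 − d/L).

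| Period | L (days) | Mean delay | Maximum delay | Missed, d = 14 | Missed, d = 28 |
|---|---|---|---|---|---|
| To Week 12 | 14 | 7 | 14 | 0 | 0 |
| Weeks 12–24 | 28 | 14 | 28 | 1 − 14/28 = 0.50 | 0 |
| Weeks 24–48 | 42 | 21 | 42 | 1 − 14/42 = 0.67 | 1 − 28/42 = 0.33 |
| After Week 48 | 84 | 42 | 84 | 1 − 14/84 = 0.83 | 1 − 28/84 = 0.67 |

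These figures apply only to episodes that an unscheduled test did see. They are not expected rates for the trial.

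**4. Direction of the error in time to resolution.** Compare all values with scheduled values only:

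- Onset at scheduled Week 30, resolution at an unscheduled Week 33 test: 3 × 7 = 21 days against 6 × 7 = 42 (Week 36). Too long.
- Onset at an unscheduled Week 27 test, still raised at Week 30, resolution at an unscheduled Week 33 test: 6 × 7 = 42 days against 42 (Week 30 to 36). No error.
- Onset at an unscheduled Week 27 test, still raised at Week 30, resolution first seen at scheduled Week 36: 9 × 7 = 63 days against 42. Too short.

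Onset can only move later. Time to resolution can move either way.

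**5. Recurrence.** Suppose Grade 3 at Week 30, Grade 1 at an unscheduled Week 33 test, and Grade 3 again at Week 36. With all values there is one resolution and one recurrence. On scheduled values alone it is a single unbroken episode with neither.

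**The case against.** The best reply is that the 3.7 rule was meant for by-visit tables only. It sits among presentation conventions, its second sentence names by-visit tables, and the laboratory sections work by date or period rather than by nominal visit. That may well be the intention. It does not settle the matter: if only by-visit tables were meant, the first sentence would be unnecessary, and nothing says that 7.2.5 is exempt.

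A second reply is that the consequence is limited. This stands. Worst grades, shifts to worst grade and listings keep unscheduled values even on the literal reading. The exposed analyses are descriptive, in a single-arm trial.

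Three stronger readings are tempting and are not supported:

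- A reader might infer that subjects with Grade 3 or 4 elevations are followed mainly by unscheduled retests, so that the rule discards most of the relevant data. The SAP gives no retest frequency. It mentions dose interruption and rechallenge, which makes off-schedule testing plausible but does not measure it.
- A reader might infer that resolution times are always overstated. The examples above show otherwise.
- A reader might extend the point to all QTc tables. Only the absolute QTc categories "will be categorized separately into the following classifications and summarized by visit"; the sentence on change categories carries no such words, the basis of shift Table 3.2.9.4 is not given, and nothing in the SAP indicates that unscheduled ECGs exist.

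**Conclusion.** The point holds as a defect in the written rule. Sections 3.7 and 7.2.5, taken together and literally, shut unscheduled ALT/AST results out of the onset, resolution and recurrence analyses. Where an event is first seen at such a test, it can be dated late by up to one scheduled interval (14, 28, 42 or 84 days, depending on time on study), or missed. The 84-day figure is a maximum and applies only after Week 48.

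That onset is late or missed needs no assumption about episode length. The mean delays and miss probabilities rest on uniform onset and on assumed durations of 14 or 28 days. The overall effect cannot be sized from the SAP, and the net bias in time to resolution can go either way.

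Tables 3.2.2.2 and 3.2.2.5 can contradict each other for any subject whose only Grade 3 or 4 value is unscheduled. The primary endpoint is not touched. This should be corrected before the safety tables are programmed.

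**What to change.** Amend the 3.7 bullet so that unscheduled assessments are excluded from by-visit summaries only. Add one sentence to 7.2.5: all post-baseline ALT/AST values, scheduled and unscheduled, are used for the onset, resolution, re-challenge and recurrence analyses.

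The cost is SAP wording and a data-selection flag. It needs no new data collection, because the analyses would use whatever unscheduled results are already in the database and due to be listed. The small downside is that subjects with more retests will have more finely dated events than others; a footnote to Table 3.2.2.5 can say so.

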### **3.7.1. Data Handling for Efficacy Endpoints**

If there is a significant degree of non-normality for a continuous endpoint, analysis may be performed on log-transformed data or using nonparametric methods, as appropriate.

### **3.7.2. Data Handling for Laboratory data**

Laboratory data that are continuous in nature but are less than the lower limit of quantitation or above the upper limit of quantitation will be imputed as follows:

- A value that is 1 unit less than the limit of quantitation will be used for calculation of descriptive statistics if the data is reported in the form of " $< x$ " (x is considered the limit of quantitation). For example, if the values are reported as  $<50$  and  $<5.0$ , then values of 49 and 4.9 will be used for calculation of summary statistics, respectively. However, for direct bilirubin, a value of " $<0.1$ " will be treated as 0.05 for calculation of summary statistics.
- A value that is 1 unit above the limit of quantitation will be used for calculation of descriptive statistics if the data is reported in the form of " $> x$ " (x is considered the limit of quantitation). For example, if the values are reported as  $>50$  and  $>5.0$ , then values of 51 and 5.1 will be used for calculation of summary statistics, respectively.
- The limit of quantitation will be used for calculation of descriptive statistics if the data is reported in the form of " $\leq x$ " or " $\geq x$ " (x is considered as the limit of quantitation).

## **3.8. Visit Windows**

### **3.8.1. Definition of Study Day 1 and Baseline**

Study Day 1 is defined as the day of first dose of study medication.

Baseline is defined as the last observation before the first dose, unless otherwise specified.

### **3.8.2. Analysis Windows**

For parameters that will be summarized by visit, the nominal visit as recorded on the electronic case report form will be used. For parameters assessed at the end of treatment (EOT) visit, the assessment results will be assigned to the next scheduled visit where the respective data were scheduled to be collected for summary. There will be no additional analysis windowing done based on the assessment date.

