### Schedule of Assessments

Period	Screen	Treatment															Follow-up		
Visit	1	2	3	4	5	6	7	8	9	10	11	12	13	14	15	16+	End of Treatment	Immediate post-treatment	Long-term
Week	-4	0	2	4	6	8	10	12	16	20	24	30	36	42	48	Q12 Weeks			
Study Day	Within -28 Days	1	15	29	43	57	71	85	113	141	169	211	253	295	337				
Visit Window		±2	±2	±2	±2	±2	±2	±2	±3	±3	±3	±3	±3	±7	±7	±7			
Informed consent	X																		
Medical history	X																		
Histopathology review	X																		
Serum virology	X																		
Coagulation	X																		
Urinalysis	X																		
β-HCG	X																		
PPD																			
HRQL – FACT-Lym		X		X		X		X	X	X	X	X	X	X	X				
Study drug return/accounting			X		X		X	X	X	X		X		X	X	X			
Adverse events		X		X		X		X	X	X	X	X	X	X	X	X	X		
Concomitant medications	X	X		X		X		X	X	X	X	X	X	X	X	X			
Performance status	X	X		X		X		X	X	X	X	X	X	X	X	X			
Vital signs	X	X		X		X		X	X	X	X	X	X	X	X	X			
Hematology	X	X	X	X	X	X	X	X	X	X	X	X	X	X	X	X			
Serum chemistry	X	X	X	X	X	X	X	X	X	X	X	X	X	X	X	X			
Pharmacodynamics		X		X		X		X	X	X	X	X	X	X	X	X			
Drug dispensing		X		X		X		X	X	X	X	X	X	X	X	X			

Period	Screen	Treatment																Follow-up		
		1	2	3	4	5	6	7	8	9	10	11	12	13	14	15	16+	Q12 Weeks	End of Treatment	Imme- di- ate post- treat- ment
Visit	1																			
Week	-4	0	2	4	6	8	10	12	16	20	24	30	36	42	48					
Study Day	Within -28 Days	1	15	29	43	57	71	85	113	141	169	211	253	295	337					
Visit Window			±2	±2	±2	±2	±2	±2	±3	±3	±3	±3	±3	±7	±7	±7				
Physical examination	X								X									X		
12-lead ECG	X								X									X		
Immunophenotyping		X				X			X		X		X		X	X	X			
Serum immunoglobulins		X				X			X		X		X		X	X	X			
Radiology assessments (CT/MRI)	X					X			X		X		X		X	X	X			
Bone marrow biopsy/aspirate a	X					X a			X a		X a		X a		X a	X a				
SPEP (IgM monoclonal protein)	X					X			X		X		X		X	X	X			
Idelalisib dosing in clinic		X		X		X			X											
Limited PK		X		X		X			X											
PPD																				

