## **7.6. Electrocardiogram Results**

The following analyses of electrocardiogram (ECG) results are intended to identify gross changes in QT intervals. The 12-lead ECG measurements will be collected at screening, Visit 9 (Week 16), and end of treatment visit.

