### **7.6.2.           Investigator Assessment of ECG Readings**

The number and percentage of subjects in the ITT analysis set with an investigator's ECG assessment of normal, abnormal and clinically significant, or abnormal but not clinically significant will be summarized for baseline and for each visit.

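### The rule that moves end-of-treatment results to the next scheduled visit does not fit ECG and physical examination: early results are tabulated as Week 16, and results after Week 16 have no defined place in the by-visit summaries.

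*SAP*

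**What the plan says.** SAP Section 3.8.2 takes the visit label recorded on the case report form as the default for by-visit summaries. For parameters assessed at EOT it then gives a specific instruction: "the assessment results will be assigned to the next scheduled visit where the respective data were scheduled to be collected for summary". It closes with "There will be no additional analysis windowing done based on the assessment date". No parameter is exempted.

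Section 7.6 sets the ECG schedule: "The 12-lead ECG measurements will be collected at screening, Visit 9 (Week 16), and end of treatment visit". In the Schedule of Assessments (Section 1.2) the physical examination row carries the same pattern of marks as the 12-lead ECG row.

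The summaries are organised by visit:
- Section 7.6.1: the absolute QTc categories "will be categorized separately into the following classifications and summarized by visit". For the descriptive statistics, "QTcB, QTcF, and uncorrected QT values at each visit and change from baseline at each visit will be summarized".
- Section 7.6.2: the investigator's ECG assessment "will be summarized for baseline and for each visit".
- Section 7.7: physical examination findings are shown by body system and visit.

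Section 3.7 confines unscheduled visits to listings and to best or worst post-baseline summaries. Section 7.6 describes no such summary for QTc.

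**The concern.** The EOT rule works when a parameter is collected often and for as long as treatment lasts: a result from a subject who stops is carried forward by at most one visit interval. ECG and physical examination have a single scheduled on-treatment visit, so the rule behaves differently on each side of it. Before Week 16 it can relabel a result by many weeks. After Week 16 it points to a visit that does not exist.

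Section 7.6 says its purpose is to detect gross changes in the QT interval. For a subject treated beyond Week 16, the EOT ECG is one of only two scheduled post-baseline readings, and the one that follows the longer exposure. If it has no place in the QTc category table, a late value above 500 msec could be absent from that table. Meanwhile the Week 16 row would mix true Week 16 readings with readings from subjects who stopped earlier.

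**Working it through.** The plan states no figure to reproduce here. The check applies the Section 3.8.2 rule to the collection schedule.

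**Inputs.** Scheduled ECG visits: screening, Visit 9 (Week 16, Day 113) and EOT (Section 7.6). Physical examination: marks at screening, Visit 9 and one late column, read as EOT because the row matches the ECG row. Treatment is open-ended (Section 1.2), so EOT can fall at any time.

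**EOT before Week 16.** The next scheduled ECG visit is always Week 16. For a subject who stops at Week 3, the displacement is 16 − 3 = 13 weeks, and it can approach 16 weeks. Hematology and serum chemistry, by contrast, are collected at every visit, so the shift is at most one interval: 2 weeks up to Week 12, 4 weeks up to Week 24, 6 weeks up to Week 48 and 12 weeks thereafter.

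**EOT after Week 16.** No later scheduled ECG or physical examination visit exists. The rule has no target, windowing by date is excluded, and no fallback is given. Radiology does not have this problem: its marks continue every 12 weeks, so there is always a next visit.

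**Other summaries that might hold these readings.**
- *QTc change categories (≤30, 31–60, >60 msec; Section 7.6.1).* They carry no by-visit wording, but they do not say which post-baseline value is used either.
- *Shift tables 3.2.9.2 and 3.2.9.4 (Section 13).* They are titles only and do not identify the post-baseline value.
- *Worst post-baseline.* Defined for laboratory grade shifts (Section 7.2.4) and Karnofsky status (Section 6.4.2.6), but not for QTc.
- *Listings.* They keep every reading (Sections 3.7 and 7.7).

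**How many subjects.** The SAP gives no time-on-treatment distribution, so the following is an illustration. Assume exponential time on drug with median m months, 125 enrolled subjects (Section 1.3), and an EOT ECG for everyone who stops. Week 16 is 112 / 30.4375 = 3.68 months and Week 24 is 168 / 30.4375 = 5.52 months.

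- Share still on drug at Week 16: S(16) = 0.5^(3.68/m). This is the share whose EOT *eventually* falls after Week 16.
- Share stopping between Weeks 16 and 24: S(16) − S(24), with S(24) = 0.5^(5.52/m). This would be the share with a late EOT if every subject had only the 24-week minimum of follow-up that triggers the final analysis.

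| Assumed median (months) | S(16) | S(24) | EOT after Week 16, eventually (of 125) | EOT after Week 16, only 24 weeks' follow-up (of 125) |
|---|---|---|---|---|
| 3 | 0.427 | 0.279 | 53 | 0.148 × 125 ≈ 18 |
| 6 | 0.654 | 0.529 | 82 | 0.125 × 125 ≈ 16 |
| 9 | 0.753 | 0.654 | 94 | 0.100 × 125 ≈ 12 |
| 12 | 0.809 | 0.727 | 101 | 0.082 × 125 ≈ 10 |

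The number at the final analysis lies between the last two columns, depending on how much follow-up beyond 24 weeks has accrued. Across the assumed medians that is about 10 to 101, which amounts to saying it is unknown. The gap in the rule does not depend on it.

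**The case against.** The strongest reply is that the SAP nowhere says late EOT data are dropped. Section 3.8.2 begins with the visit recorded on the case report form, and Section 7.6 names EOT as a collection visit. Where no next visit exists, a programmer could reasonably conclude that the reassignment cannot operate and keep an EOT row. That stands. A reader might infer that the plan discards late QTc data, and the text does not support that: placement is undefined, loss from the by-visit tables follows only from literal application, and the listings keep the readings. What survives is that the specific EOT sentence makes no allowance for this case, so the tables depend on an unwritten choice.

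Second, carrying an early EOT result forward is the declared purpose of the rule, and a subject who stopped at Week 3 has no true Week 16 reading to displace. That is also fair. The convention is explicit, but the displacement is far larger here than for frequently collected parameters, and it changes what the Week 16 QTc row means.

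Third, a reader might take most of the 125 subjects to be affected. That would ignore those still on treatment at the data cutoff, a category Section 4.2 itself reports. Nor does the SAP support calling the EOT ECG an on-drug reading, since it does not say whether the ECG precedes or follows the last dose.

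Finally, the physical examination part rests on a schedule table damaged in extraction and on its match with the ECG row; no sentence in the SAP states those visits.

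**Conclusion.** The point holds as a mismatch between a general rule and a sparse schedule. For ECG, the text alone establishes that EOT results before Week 16 are tabulated as Week 16 whatever their date, and that EOT results after Week 16 have no target visit. For physical examination the same follows if its late mark in the schedule is EOT. No QTc summary is defined that would certainly capture late EOT or unscheduled ECGs, because the change categories and shift tables leave the post-baseline value unspecified.

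The number of subjects affected at the final analysis cannot be derived from the SAP. The consequence is limited to how cardiac safety and examination findings are tabulated; no efficacy result, error rate or primary conclusion is touched. It is a minor correction, worth making because the QTc tables exist to reveal extreme values.

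**What to change.** Add a sentence to Section 3.8.2 exempting ECG and physical examination from the reassignment rule, with EOT summarized as its own row in the Section 7.6.1, 7.6.2 and 7.7 tables. In Section 7.6.1, add a worst post-baseline summary of the QTc categories and of the QTc change categories, using all post-baseline ECGs including EOT and unscheduled ones. This also provides the kind of summary to which Section 3.7 admits unscheduled readings. State in the same place which post-baseline value Tables 3.2.9.2 and 3.2.9.4 use.

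The cost is a sentence or two in the SAP and a few extra table rows. No new data are needed. The Week 16 row will contain fewer subjects, but all of them will have been measured at that visit.
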